5. SAMPLE SIZE CALCULATIONS

The required sample size is 1120 patients. With 90% power at a p value of 0.05 with a 3% dropout, 560 per group will be required to detect a 23% relative reduction (9% absolute reduction) in 90 day mortality, assuming a control group mortality of 41%. This sample size would also detect a 20% relative reduction (8% absolute reduction) at 80% power.

We have used two independent sources for the estimation of the all-cause mortality that was used to determine the sample size:

- 1. Data from the Intensive Care National Audit and Research Centre (ICNARC) case mix programme (CMP) for UK intensive care patients. The unpublished ICNARC data from the CMP for the year 2012 was compiled from 133,266 admissions from 203 adult critical care units in England, Wales and Northern Ireland. For patients with a PaO_2/FiO_2 ratio < 20kPa the ICU mortality was 40.7% and the hospital mortality was 48.8%.
- 2. Data from the NIHR HTA funded OSCAR trial (30). This was a recent large randomised controlled trial on high frequency oscillatory ventilation (HFOV) in patients with respiratory failure. The 30-day mortality in the control group in the OSCAR trial was 41.1%. These patients received conventional ventilation with a tidal volume of 6-8ml/kg PBW and had an average PaO₂/FiO₂ ratio of 15kPa.

Doc No: ST06-RD01 Page **14** of **35** We have assumed 90-day control group mortality will be at least equivalent to 41%. We have

used the effect size of one of the few interventions to reduce mortality in patients with

hypoxaemic respiratory failure. The ARDSNet ARMA trial demonstrated a 9% absolute risk

reduction in patients with hypoxaemic respiratory failure secondary to ARDS with lung

protective ventilation. Our hypothesis is that we can extend the benefits of more protective

lung ventilation with the use of ECCO₂R. Loss to follow up in UK critical care trials is low. We

know this is approximately 3% from previously published research as well as from the

experience of our team in managing large critical care trials in the UK.

An independent statistician (for the DMEC) will conduct an interim analysis for the primary

outcome measure (mortality) before the recruitment of 560 patients; (half the estimated

sample size), to ascertain whether the assumptions made in the sample size calculations are

correct.

6. RANDOMISATION AND BLINDING

6.1 Randomisation

Once consent has been obtained for the patient to participate in the study the patient will be

randomised to either ECCO₂R with lower tidal volume mechanical ventilation or standard care.

Patients will be randomised via a central randomisation system and sites will be provided with

trial specific randomisation guidelines. Randomisation will be completed by an appropriately

trained and delegated member of the research team.

Randomisation will be stratified by recruitment centre.

Participants will be allocated to ECCO₂R with lower tidal volume mechanical ventilation or

standard care on a 1:1 ratio. At the time of randomisation, each patient will be allocated a

unique Participant Study Number, which will be used throughout the study for participant

identification. An entry will be recorded in the patient medical notes noting enrolment into the

study.

Doc No: ST06-RD01

Page **15** of **35**

The research team will then ensure that the clinical team are informed which treatment this process has allocated. They will liaise with the clinical team as required to ensure that the allocated treatment is administered. If allocated VV-ECCO₂R, this should ideally be commenced within 8 hours of randomisation.

6.2 Blinding and Allocation Concealment

Only the allocation of the intervention will be concealed; once assigned to the standard care or intervention group the interventions will be unblinded to the trial participant's representative (and to the participant on regaining capacity), research team, care providers, data analysts and outcome assessors. By the nature of the intervention it will not be possible to blind clinicians to whether a participant has been randomised to ECCO₂R or standard care.

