2. OUTCOME MEASURES

2.1 Primary outcome measure(s)

All cause mortality 90 days after randomisation

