2.2 Secondary outcome measures

- I. Tidal volume (ml/kg PBW) at day 2 and day 3 after randomisation
- II. Ventilator free days at 28 days after randomisation
- III. Duration of ventilation in survivors after randomisation at 28 days
- IV. Need for ECMO up to Day 7
- V. Mortality rate at 28 days, 6 months and 1 year after randomisation
- VI. Health Related Quality of Life (HRQoL) at 6 months and 1 year after randomisation
- VII. Adverse event rate
- VIII. Health & Social Care Service costs at 6 months and 1 year
 - IX. St George's Respiratory Questionnaire (SGRQ) at 1 year and need for home oxygen at 6 months and 1 year after randomisation
 - X. Post Traumatic Stress Syndrome Questionnaire (PTSS-14) at 1 year after randomisation
- XI. Montreal Cognitive Assessment (MoCA-BLIND) or AD8 Dementia Screening Interview (AD8) at 1 year after randomisation

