- CO₂ removal rate while on ECCO₂R therapy
- Commencement or transfer for ECMO following randomisation
- Use of adjunctive therapies including NMBD and prone positioning
- Blood product administration (blood, platelets, fresh frozen plasma, cryoprecipitate or other)
- Adverse events

Day 1 and 2:

Echocardiography parameters including but not limited to ventricular size and function and TAPSE.

Doc No: ST06-RD01 Page **11** of **35**

Day 3 and 7

• Determinants of SOFA score

28 days:

Adverse Events

6 months:

- EuroQoL-5 Dimension Questionnaire (EQ-5D-5L) (Post or telephone)
- Patients use of health and social care resources collected by resource logs

1 year:

- EQ-5D-5L (Post or telephone)
- Patients use of health and social care resources collected by resource logs
- SGRQ
- PTSS-14
- MoCA-Blind or AD8

The following data will also be collected

- Date of discontinuation of ECCO₂R and reason
- Date of discontinuation of mechanical ventilation (unassisted breathing)
- Date of critical care discharge
- Date of hospital discharge
- Date of death

Follow Up Visits and Procedures

HRQoL and Health and Social Care Service use will be assessed at 6 months and 1 year after randomisation. Patients will also be required to complete the SGRQ at 1 year.

The CTU will also collect mortality data at 1, 2 and 5 years post randomisation.

Doc No: ST06-RD01 Page **12** of **35**

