7. ANALYSIS PRINCIPLES

The primary analysis will be conducted on all outcome data obtained from all participants as randomised and regardless of protocol adherence, i.e. intention to treat analysis.

Standard approaches will be used to detect patterns in missing data. Baseline characteristics, follow-up measurements and safety data will be described using the appropriate descriptive summary measures depending on the scale of measurement.

For the primary outcome and other dichotomous outcomes, risk ratios and 95% confidence interval (CI) will be calculated. The primary outcome of 90 day mortality will be analysed using chi-square and a secondary analysis using logistic regression to adjust for age, SOFA score, Baseline PaO_2 / FiO_2 and Baseline Plateau Pressure will also be carried out. The comparison of continuous outcomes between the two groups will be investigated using analysis of variance/analysis of covariance (if baseline measurements available), adjusting for other covariates where appropriate. Time-to-event outcomes will be analysed by survival methods and reported as hazard ratios with 95% CI. The intention-to-treat basis analysis will use a significance level of <0.05 for the primary outcome. Sensitivity analysis will be performed for the primary outcome excluding the first two intervention arm patients at each site in order to address potential learning effects. This would be explored further using a power curve model.

Doc No: ST06-RD01 Page **16** of **35**

Per protocol analysis will also be carried out for the secondary outcome of Tidal Volume at Days 2 and 3 i.e. including those who were on VV-ECCO₂R on day 2 and 3 in the intervention arm. Estimates of effects/association and 95% CI will be reported for secondary and exploratory outcomes.

An independent statistician (for the DMEC) will conduct an interim analysis for the primary outcome measure before the recruitment of 560 patients. Using the chi-square statistic (mortality by treatment group), a p value less than 0.001 will be used according to the Haybittle-Peto stopping rule.

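### Section 6.2 leaves outcome assessors and data analysts unblinded for a reason that covers only clinicians, which exposes the interview- and telephone-collected secondary outcomes and one open analysis choice

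*SAP*

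**What the plan says.** SAP section 6.2 conceals the allocation only up to assignment. After that it is open to "research team, care providers, data analysts and outcome assessors", and also to the participant's representative and to the participant on regaining capacity. One reason follows: "By the nature of the intervention it will not be possible to blind clinicians". None is given for analysts or assessors.

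The primary outcome (section 2.1) is "All cause mortality 90 days after randomisation", and section 7 fixes its test: "The primary outcome of 90 day mortality will be analysed using chi-square".

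Among the secondary outcomes, section 2.2 lists "Montreal Cognitive Assessment (MoCA-BLIND) or AD8 Dementia Screening Interview (AD8) at 1 year after randomisation". Section 3.3 has EQ-5D-5L collected by post or telephone at 6 months and 1 year. It gives no mode of collection for SGRQ, PTSS-14, MoCA-Blind or AD8.

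For continuous outcomes, section 7 allows analysis of variance or covariance, "adjusting for other covariates where appropriate", without listing those covariates.

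The SAP provides no masked assessor, coded arms or blind data review for the final analysis. The independent statistician in sections 5 and 7 handles only the interim look.

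**The concern.** An open-label device trial cannot mask the bedside, but it can often mask the person who telephones a survivor months later and the person who runs the models. Section 6.2 gives up both on an argument that covers neither.

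An assessor who knows the arm may prompt or score differently, and a small systematic difference is enough to move a comparison of means. An analyst who knows the arm and has an open covariate list may, without intent, settle on the adjustment that looks better. At stake are the 1-year cognitive outcome and, through telephone EQ-5D-5L, secondary objective v (health-related quality of life).

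**Working it through.** **1. The plan's own figure.** The concern does not depend on the sample size, but the illustration in step 4 starts from it. Inputs from section 5: control mortality 41%, relative reduction 23%, power 90%, alpha 0.05 (taken as two-sided, since sidedness is not stated), dropout 3%.

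- p1 = 0.41; p2 = 0.41 × 0.77 = 0.3157; mean p = 0.36285.
- n = [1.96·√(2·p(1−p)) + 1.2816·√(p1(1−p1) + p2(1−p2))]² / (p1−p2)², with p the mean
- n = (1.333 + 0.867)² / 0.0943² = 4.840 / 0.008892 = 544.3, so 545 per arm.
- With dropout: 545 / 0.97 = 561.9, so 562 against the stated 560. The figure reproduces.

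Blinding changes neither this number nor power or alpha.

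**2. Does the stated reason reach each group left unblinded?**

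| Group in section 6.2 | Covered by the reason given? |
|---|---|
| Care providers | Yes |
| Research team at the bedside | In practice yes, as section 6.1 has them tell the clinical team the allocation |
| Outcome assessors at 6 months and 1 year | No |
| Data analysts | No |

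**3. Which results depend on the last two groups?**

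- 90-day mortality: an objective event with a fixed, unadjusted test. Not exposed.
- AD8: an interview by its own name in section 2.2. Exposed.
- MoCA-BLIND: no mode stated. Exposed only if an interviewer administers it.
- EQ-5D-5L: exposed only for the unknown share taken by telephone.
- SGRQ and PTSS-14: called questionnaires, with no mode stated. The SAP gives no basis for including them.
- Continuous outcomes generally: exposed through the unlisted covariates.

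**4. Illustration of size.** Assumptions, none of them from the SAP: 50–80% of survivors are assessed; 90-day survival stands in for 1-year survival; there is no true difference in score; knowledge of the arm shifts the mean score by b standard deviations.

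- Survivors at the planned rates: control 560 × 0.59 = 330.4; intervention 560 × 0.68 = 380.8 (mortality 41% − 9% = 32%).
- SE in SD units = √(1/n1 + 1/n2).
- Chance of p < 0.05 = Φ(b/SE − 1.96) + Φ(−b/SE − 1.96).

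| Assessed | n1 | n2 | SE | b = 0.05 | b = 0.1 | b = 0.2 |
|---|---|---|---|---|---|---|
| 50% | 165 | 190 | 0.106 | 8% | 16% | 47% |
| 80% | 264 | 305 | 0.084 | 9% | 22% | 66% |

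Example: with 50% assessed and b = 0.1, b/SE = 0.94, and Φ(−1.02) + Φ(−2.90) = 0.154 + 0.002 = 0.156.

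The b = 0.05 column is what a 0.1 SD shift becomes if it acts on only half of the responses, for example if half of the EQ-5D-5L forms come by post.

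**The case against.** The strongest reply is that this is a disclosed choice in a trial that section 1 calls open and pragmatic. Nothing is misstated, the primary outcome is death, and who makes follow-up calls is a conduct matter that the protocol may settle. Participants know their arm, so masking callers cannot remove bias from self-report. The analyst is already constrained. Section 7 fixes intention to treat, the learning-effect exclusion, the per-protocol definition for tidal volume and the covariates for adjusted mortality, and section 7.1 lists the subgroups.

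Much of this stands. It limits the point to a few secondary outcomes and one open choice. It does not remove the point, because the SAP itself states that assessors and analysts are unblinded, and disclosure is not a reason.

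Four stronger readings are tempting, and the document does not support them:

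- *The mortality result is at risk.* It is an objective event tested by a fixed chi-square.
- *Objective viii (respiratory morbidity) is at risk.* Section 2.2 measures it by SGRQ and home oxygen, and no interviewer is documented for either.
- *The analyst could choose exclusions to suit an arm.* Section 7 largely fixes populations and exclusions. The power curve model for learning is unspecified, but it follows on from a sensitivity analysis defined on intervention-arm patients, so masking would not repair it.
- *The false-positive rate would rise to about 36%.* That needs an SD of 4, a bias of 0.5 points and a MoCA-BLIND score for all 330 survivors per arm: SE = 4 × √(2/330) = 0.31, shift 1.6 SE. The SD and bias are assumed. Section 2.2 offers MoCA-BLIND or AD8, so one instrument need not cover everyone.

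Section 7 also sets a significance level only for the primary outcome and plans estimates with intervals for the rest. The draft main-outcome table in Appendix 3 nevertheless has a p-value column with rows for MoCA-Blind and AD8. Without a p-value, the same shift would displace the estimate and its interval.

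**Conclusion.** The point holds in limited form. Section 6.2 leaves assessors and analysts unblinded without a reason that applies to them. This creates an avoidable exposure for the AD8, for MoCA-BLIND if interviewer-administered, for the telephone share of EQ-5D-5L, and for the choice of covariates for continuous outcomes.

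The SAP does not allow the bias to be estimated. Under the stated assumptions, a 0.1 SD shift takes a nominal 5% false-positive rate to about 16–22%. The result is sensitive to the assumed shift: 8–9% at 0.05 SD and 47–66% at 0.2 SD. For a given shift the figures lean high, because deaths between 90 days and 1 year and the split between two cognitive instruments both reduce the numbers scored. They show that a modest shift would matter at this sample size, not that one will occur.

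This is a cheap improvement to secondary outcomes and not a threat to the trial's main conclusion.

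**What to change.** - **Assessors.** Amend section 6.2 so that follow-up staff who administer or score AD8, MoCA-BLIND and telephone EQ-5D-5L work from a contact list without the allocation, ask respondents not to disclose it, and record any unmasking. If that is impracticable, give a reason that applies to these staff.
- **Covariates.** In section 7, list the covariates for the continuous outcomes before the analyst sees outcome data by arm.
- **Analyst.** Where practicable, run the first analysis of the follow-up questionnaires under dummy A/B codes. Run analyses that need or reveal the true arm after the codes are broken: the learning-effect sensitivity analysis, per-protocol tidal volume, ECCO₂R use and device effects.

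**Cost.** SAP and working-instruction wording, a contact list without the arm field, and a set order of analyses; no added patients or visits. Someone other than the analyst must hold the code key and keep arm-revealing fields out of the questionnaire dataset. That needs arranging, because section 3.2 involves the study statistician in data extraction. Masking will be partial and self-report bias will remain.

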7. ANALYSIS PRINCIPLES

The primary analysis will be conducted on all outcome data obtained from all participants as randomised and regardless of protocol adherence, i.e. intention to treat analysis.

Standard approaches will be used to detect patterns in missing data. Baseline characteristics, follow-up measurements and safety data will be described using the appropriate descriptive summary measures depending on the scale of measurement.

For the primary outcome and other dichotomous outcomes, risk ratios and 95% confidence interval (CI) will be calculated. The primary outcome of 90 day mortality will be analysed using chi-square and a secondary analysis using logistic regression to adjust for age, SOFA score, Baseline PaO_2 / FiO_2 and Baseline Plateau Pressure will also be carried out. The comparison of continuous outcomes between the two groups will be investigated using analysis of variance/analysis of covariance (if baseline measurements available), adjusting for other covariates where appropriate. Time-to-event outcomes will be analysed by survival methods and reported as hazard ratios with 95% CI. The intention-to-treat basis analysis will use a significance level of <0.05 for the primary outcome. Sensitivity analysis will be performed for the primary outcome excluding the first two intervention arm patients at each site in order to address potential learning effects. This would be explored further using a power curve model.

Doc No: ST06-RD01 Page **16** of **35**

Per protocol analysis will also be carried out for the secondary outcome of Tidal Volume at Days 2 and 3 i.e. including those who were on VV-ECCO₂R on day 2 and 3 in the intervention arm. Estimates of effects/association and 95% CI will be reported for secondary and exploratory outcomes.

An independent statistician (for the DMEC) will conduct an interim analysis for the primary outcome measure before the recruitment of 560 patients. Using the chi-square statistic (mortality by treatment group), a p value less than 0.001 will be used according to the Haybittle-Peto stopping rule.

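### The learning-effect sensitivity analysis of 90-day mortality drops early patients from the ECCO2R arm only, so it cannot separate learning from time or site effects

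*SAP*

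**What the plan says.** SAP Section 7 bases the primary analysis on "all outcome data obtained from all participants as randomised and regardless of protocol adherence, i.e. intention to treat analysis". Ninety-day mortality "will be analysed using chi-square and a secondary analysis using logistic regression to adjust for age, SOFA score", baseline PaO2/FiO2 and baseline plateau pressure.

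The same section plans one analysis that it calls a sensitivity analysis of the primary outcome: "excluding the first two intervention arm patients at each site in order to address potential learning effects". It removes no controls and specifies no site or calendar-time term for this comparison. The follow-on is one sentence: "This would be explored further using a power curve model".

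On the design, Section 6.1 states "Randomisation will be stratified by recruitment centre", with allocation between ECCO2R and "standard care on a 1:1 ratio". Section 7.1 (iv) adds an exploratory subgroup by centre volume, split at 10 ECCO2R participants.

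**The concern.** Enrolment order within a site defines the exclusion, but it is applied to one arm. Three things follow.

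- The remaining ECCO2R patients are all later patients, while the controls are a mixture of early and later ones. If case mix, patient selection or general care shifts while a site starts up, both arms feel it, but only the control arm still carries it.
- The 1:1 balance within centre is lost, most of all at small centres. Where a centre has fewer than 10 ECCO2R patients, a category that Section 7.1 (iv) allows for, at least 2/9 (22%) of its ECCO2R patients leave and none of its controls do. If small centres differ in risk, this alone shifts the comparison.
- A centre with two or fewer ECCO2R patients supplies controls with nothing to compare them against.

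The analysis is there to address learning with the device. Built this way, a change from the primary result could reflect learning, a time trend or a change in the mix of sites, and the analysis cannot tell the reader which.

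**Working it through.** **Inputs from the SAP.** 560 per arm, control mortality 41% and a target of 9 points absolute (Section 5); 1:1 allocation stratified by centre (Section 6.1); two ECCO2R patients removed per site (Section 7).

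**Assumptions.** S = 20 to 40 sites. Early patients in both arms have mortality d points above later ones, with d = 5 to 10, and the sign also reversed. There is no true treatment effect. Tests are two-sided at 5% (the SAP does not state sidedness).

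**The plan's own figure.** The SAP gives none for this analysis, but the 560 used as denominator reproduces. With p1 = 0.41 and p2 = 0.41 × 0.77 = 0.3157, the pooled-variance formula at 90% power gives 545 per arm, and 545 / 0.97 = 562.

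**Bias.** The share of the ECCO2R arm removed is f = 2S/560. Overall mortality is 0.41 in each arm, so later patients have mortality 0.41 − f × d. After the one-arm exclusion:

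- difference (ECCO2R minus control) = −f × d
- risk ratio = (0.41 − f × d) / 0.41

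As a scale for this bias, the chance of a nominally significant benefit under the null is Φ[(f × d − 1.96 × SE0) / SE1], where SE0 is the pooled and SE1 the unpooled standard error for 560 − 2S against 560 patients.

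For S = 40 and d = 10 points:

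- f = 80/560 = 0.143; difference = −0.143 × 10 = −1.43 points; risk ratio = 0.3957/0.41 = 0.965
- SE0 = 0.0305 and SE1 = 0.0305
- Φ[(0.0143 − 0.0598)/0.0305] = Φ(−1.49) = 6.8%

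| Sites | Early excess d (points) | Share removed | Difference (points) | Risk ratio | Chance of significant benefit |
|---|---|---|---|---|---|
| 20 | +5 | 7.1% | −0.36 | 0.991 | 3.3% |
| 20 | +10 | 7.1% | −0.71 | 0.983 | 4.3% |
| 40 | +5 | 14.3% | −0.71 | 0.983 | 4.2% |
| 40 | +10 | 14.3% | −1.43 | 0.965 | 6.8% |
| 20 | −10 | 7.1% | +0.71 | 1.017 | 1.4% |
| 40 | −10 | 14.3% | +1.43 | 1.035 | 0.8% |
| 20 or 40 | 0 | as above | 0 | 1.000 | 2.5% |

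The bias is therefore 0.36/9 = 4% to 1.43/9 = 16% of the target effect.

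**Unequal sites.** The algebra assumes that every site has at least two ECCO2R patients. A simulation with 40 sites of unequal size (4,000 runs per scenario) gave −1.3 points for d = +10 and +1.3 points for d = −10. With no time trend, but risk rising by 5 points per standard deviation as log site size falls, the bias was −0.5 points and the chance of a significant benefit 3.9%.

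**Symmetric exclusion.** When the first two patients in each arm were removed at every site, the mean difference stayed within about 0.1 point of zero in every simulated scenario. The chance of a significant benefit was 2.1% to 2.6%.

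**Dependence on trial size.** The number removed depends on sites, not on patients. At 280 per arm (half of 560), the same 40 to 80 exclusions would be 14% to 29% of the ECCO2R arm, and the largest bias in this range would be 0.286 × 10 = 2.9 points.

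**The case against.** The strongest defence is that learning with the device can only affect the arm that receives it. If there is no shared trend and no link between site size and risk, keeping all controls is unbiased and slightly more precise. That is correct, but the SAP gives no ground for assuming either condition, and the analysis is informative only if they hold.

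The SAP also does not rely on this analysis alone. It names a power curve model and a treatment-by-centre-volume interaction. These reduce the weight on the exclusion rule but do not repair it: the model has no stated form and no stated handling of controls, and the subgroup answers a different question. The adjusted logistic regression has no site or time term.

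A reader might infer that the rule is built to produce a benefit. The documents do not support that. The bias depends on trends the SAP does not describe, can equally hide a benefit, and is modest over the assumed range.

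A reader might also extend the point to the per protocol tidal-volume analysis, which restricts to patients on the device "on day 2 and 3 in the intervention arm". That is a separate matter. It concerns a secondary outcome, has nothing to do with enrolment order, and is reported beside the all-patient comparison (Section 8.5 and the Appendix 3 table). Nothing worked out here bears on it.

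**Conclusion.** The exclusion rule is wrong as written and should be fixed. It breaks the centre-stratified comparison and cannot distinguish a learning effect from a time or site effect.

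The size, about 0.4 to 1.4 points in either direction, rests wholly on the assumed 20 to 40 sites and the assumed 5 to 10 point early difference in both arms.

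It would go too far to conclude that the trial's main result is at risk. The primary analysis keeps everyone as randomised, the intention-to-treat analysis is the one that "will use a significance level of <0.05 for the primary outcome", and the interim stopping rule uses mortality by treatment group without this exclusion. No decision rule rests on the sensitivity analysis, so the probabilities above measure the bias and are not trial error rates.

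**What to change.** Reword the rule in Section 7 so that, at each site, all patients in both arms randomised up to and including that site's second ECCO2R patient are excluded. Removing the first two patients in each arm at each site is an acceptable alternative. Compare the remaining patients stratified by site. Stratifying while keeping the one-arm exclusion would deal with site differences but not with a shared time trend.

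Dropping the first four patients at a site whatever their arm is not equivalent. Section 6.1 gives no block size, and under simple 1:1 allocation the chance of fewer than two ECCO2R patients among four is (1 + 4)/16 = 5/16, or 31% of sites. Early device patients would then remain.

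The cost is one sentence and about two controls per site, so 40 to 80 controls at 20 to 40 sites. With equal event rates and m = 560 − 2S patients left per arm, the interval widens by a factor of √[1120/(560 + m)]. That is √(1120/1080) = 1.02 at 20 sites and √(1120/1040) = 1.04 at 40 sites. The primary analysis does not change.
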